Exclusion criteria	
1. Subjects with infested household members do not agree to take part in the study or receive the Standard of Care treatment.2. History of irritation or sensitivity to Natrum Muriaticum 2X (HPUS) or Vamousse Spray 'n' Go components, pediculicides or hair care products.3. Presentation at the treatment site with visible skin/scalp condition(s) that are not attributable to head lice infestation, such as an erythema score and atopic dermatitis that is >2, blisters, vesicles which, in the opinion of the investigative personnel or medical monitor, will interfere with safety and/or efficacy evaluations.4. Children under two years old.5. Use of any chemical, physical or mechanical lice removal treatment in any subject following diagnosis.6. Treatment for head lice (Over the counter [OTC], home remedy and/or Prescription) in the last 7 days.7. Any condition or illness that, in the opinion of the investigator, may compromise the objective of the protocol.8. Females who are pregnant, nursing or planning a pregnancy which could include subjects. If a household has a pregnant female who has an active case of lice, the entire household is excluded from participation.9. Subject of child-bearing potential, and unwilling to use an adequate method of contraception for the duration of the study. Adequate methods of contraception include: abstinence, vasectomized partner, oral birth control pills, birth control injections or patches, Intra uterine devices, condoms with a spermicidal jelly or a diaphragm with spermicidal jelly, surgical sterilization. Subjects and/or their caregivers will be considered non-child-bearing if the following has occurred: full hysterectomy or bilateral oophorectomy is considered surgically sterile. Tubal ligation is not considered equivalent to female sterilization.10. Participation in a previous investigational drug study within the past 30 days.11. Does not understand the requirements for study participation and/or may likely exhibit poor compliance, in the opinion of the investigator.12. Does not have a known household affiliation with their household members (i.e., do not stay in one household consistently, sleeping at one place several nights and then at another place or location). Household is defined as living in a shared area or space (for example the same house or apartment unit).

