5.5 Subject withdrawal and termination

5.5.1 Potential reasons for withdrawal

In accordance with the Declaration of Helsinki and other applicable regulations, a subject has the right to withdraw from the study at any time and for any reason without prejudice to his or her future medical care. The Investigator or Medical Monitor may also withdraw the subject at any time if it is medically necessary or in the interest of subject safety.

A subject will be discontinued from this study if any of the following criteria are met:

1. Withdrawal of consent by the subject is received. In the opinion of the Investigator or Medical Monitor it is not in the subject's best interests to continue in the study.
2. Occurrence of an Adverse Event (AE) or Serious Adverse Event (SAE), which, in the opinion of the Investigator, warrants discontinuation of the subject from the study.
3. Pregnancy as informed by the subject or as determined by a positive urine pregnancy test.
4. Significant non-compliance with study procedures that would interfere with the study results or increase the subject's risks in the study, as determined by the Investigator.
5. Subject is deemed to be a treatment failure if upon revisit it is determined that they are still infested having live lice. They will be terminated from the study and provided the standard of care at that point in the study.
6. Any clinical adverse event (AE), laboratory abnormality, or other medical condition or situation occurs such that continued participation in the study would not be in the best interest of the participant.
7. The participant meets an exclusion criterion (either newly developed or not previously recognized) that precludes further study participation.

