7.5 Prohibited medication, treatment and procedures

Head lice treatment products (over the counter [OTC], home remedy and/or Prescription) are prohibited 30 days prior to and during the study. These include, but are not limited to:

- Nix Ultra
- Rid Max
- LiceMD

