10.2 Data sets to be evaluated

The subject populations are defined as follows:

Safety Population includes all subjects who were administered treatment. This is the population that will be used for the safety assessments.

Modified Intent-to-Treat (mITT) population includes all subjects who met all inclusion/exclusion criteria, were randomized, administered treatment, and had at least one post-treatment efficacy evaluation. This is the primary population for determination of the effectiveness of the active treatment.

Per-Protocol (PP) population includes all mITT subjects who were administered treatment, had no protocol deviations which could have interfered with the accurate assessment of treatment efficacy, and returned for the Day 14 visit within the allowed window. This is the primary population for the efficacy comparisons between the two active treatment groups.

Subjects whose condition worsens and require alternate or supplemental therapy for the treatment of head lice during the study will be discontinued, included in both the mITT and PP population analyses as treatment failures. Subjects who discontinue early for reasons other than treatment failure will be excluded from the PP population, but included in the mITT population, using Last Observation Carried Forward (LOCF).

Efficacy analyses will be performed on both the per-protocol population and the mITT population. Safety analyses will be performed using the Safety population as defined.

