10.5 Sample Size

Sample size is 52. The requisite sample size for the *t*-test of the means of independent samples, assuming a Cohen's *d* of .40, alpha .05 two-tailed, and a power of .80, was smaller at 44. Thus, the larger requisite sample size for the *z*-test will also suffice for the *t*-test and will provide a cushion for the application of the Holm correction for Type I error. The sample size of 52 should be increased to account for a 10% expected dropout rate, resulting in a total sample size, rounded to an even number, of 58 (26 per group).

Expected difference:

40% difference between treatment groups, based on results of LiceFreee Spray (1% Sodium Chloride) compared to Permethrin; the results showed significantly higher pediculicidal activity for Sodium Chloride spray (85%) as compared to Permethrin (45%) at Day 15 ($p < 0.05$)¹.

A pilot study using Vamousse Spray 'n' Go as a once only treatment, showed high early lice kill (88% lice free at day 0 after treatment) but low efficacy at day 14 (12% lice free). It is anticipated that repeat dosing after 7 days, if live lice are present, will boost day 14 efficacy to levels similar to those at day 0.

Assumptions:

80% power, 0.05 alpha
Allocation ratio 1:1

Methods:

Calculations performed in Stata/IC 16.1
Binary data (lice free – Y/N) – proportions
Independent samples
Chi Squared, two-sided test

Sample:

Estimated sample sizes for a two-sample proportions test
Pearson's chi-squared test
 $H_0: p_2 = p_1$ versus $H_a: p_2 \neq p_1$
Study parameters:

```
alpha = 0.0500
power = 0.8000
delta = 0.4000 (difference)
p1 = 0.4500
p2 = 0.8500
```

Estimated sample sizes:

$N = 52$
 N per group = 26
Allowance for drop out: 10% per group, 3
Total sample: 29 per group (58)

References:

¹ Serrano, L. et al. Evaluation of the Efficacy and Safety of 1% Sodium Chloride (LiceFreee Spray) against 1% Permethrin Crème Rinse on Head Lice Infested Individuals. *Pharmacology & Pharmacy*, 2013, 4, 266-273.

11 Source documents and access to source data/documents

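### Section 10.2 has no single outcome rule for use of a prohibited lice product, so a subject last seen lice free can be carried forward as a Day 14 success

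*Combined protocol and SAP*

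**What the plan says.** **The prohibition.** Section 7.5 says that other head lice products "are prohibited 30 days prior to and during the study". The synopsis (exclusion 5) also lists "Use of any chemical, physical or mechanical lice removal treatment in any subject following diagnosis". Section 5.2 has no such item; its nearest equivalent is prior treatment in the last 30 days.

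**The discontinuation.** Section 5.5.1 ends participation for significant non-compliance (item 4) and, in item 7, where "The participant meets an exclusion criterion (either newly developed or not previously recognized) that precludes further study participation". Neither item assigns an analysis outcome. Item 5 makes live lice found at a revisit a treatment failure.

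**The analysis.** Section 10.2 contains three relevant statements.

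- mITT "includes all subjects who met all inclusion/exclusion criteria, were randomized, administered treatment" and had at least one efficacy evaluation after treatment. No time point is given for meeting the criteria.
- "Subjects whose condition worsens and require alternate or supplemental therapy for the treatment of head lice during the study will be discontinued" and counted as failures in both mITT and PP.
- Subjects who discontinue early for any reason other than treatment failure leave PP and stay in mITT by LOCF.

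The PP definition in the same section also drops subjects with deviations that could interfere with the efficacy assessment. The synopsis calls mITT primary and PP secondary. Section 10.2 calls PP the primary population for comparing the two groups, so both populations matter.

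**The concern.** Using another lice product is often a sign that the assigned treatment has not worked. Section 10.2 makes such a subject a failure only when two conditions are met: the condition has worsened, and other therapy is required.

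Take a subject who is lice free at Day 2, whose caregiver then applies a shop product, and for whom the site records no relapse. Discontinued for non-compliance, this subject falls under the rule for other reasons, and the lice-free Day 2 reading becomes the Day 14 result in mITT. In PP the subject is dropped if the use is treated as an interfering deviation, but included as a failure if it is treated as alternate therapy.

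The other failure clauses do not reliably catch this subject. Item 5 of 5.5.1 needs live lice at a revisit, and the shop product may already have removed them. The report-based failure rule in 4.1 starts only after Day 7. Sections 7.3.4 and 7.6 concern Day 14.

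The trial is open-label, so both the decision to self-treat and its later classification can depend on the known assignment.

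**Working it through.** **Inputs.** From 10.5: control 45%, spray 85%, two-sided alpha 0.05, power 80%, "Allocation ratio 1:1", test given as "Chi Squared, two-sided test", "Allowance for drop out: 10% per group, 3", so 29 per arm. The pilot figures (88% and 12%) are also from 10.5. The test is the Z test for independent proportions (10.1, 10.4.2). The number of subjects using other products is not in the documents, so all such counts below are assumptions.

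**1. The plan's own sample size.** Without continuity correction, with mean rate 0.65:

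n = [1.960 × √(2 × 0.65 × 0.35) + 0.842 × √(0.45 × 0.55 + 0.85 × 0.15)]² / 0.40² = (1.322 + 0.515)² / 0.16 = 21.1, or 22 per group.

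With continuity correction:

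(21.1 / 4) × [1 + √(1 + 4 / (21.1 × 0.40))]² = 25.9, or 26 per group, 52 in total.

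This is the plan's figure. Allowing for 10% dropout, 26 / 0.9 = 28.9, or 29 per group (58). The present point does not change it.

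**2. Effect of one subject.** Moving one subject from failure to LOCF success adds 1/29 = 3.4 points to that arm. For 1 to 6 such subjects, all last seen lice free, the range is 3.4 to 20.7 points (6/29). If only 88% of them were last seen lice free (the pilot's early rate, borrowed as an assumption), it is 3.0 to 18.2 points (6 × 0.88 / 29).

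**3. Assumed case in the spray arm.** Control is 13/29 = 44.8%. Three spray subjects use another product after a lice-free visit, a number chosen to match the dropout allowance. Twenty other spray subjects are successes. The statistic is z = (p1 − p2) / √[p(1 − p)(1/n1 + 1/n2)], with p the pooled rate.

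| Handling of the three | Spray | Pooled p | z | Two-sided p |
|---|---|---|---|---|
| Failures (mITT or PP) | 20/29 = 69.0% | 33/58 | 0.241 / 0.130 = 1.86 | 0.063 |
| Dropped (PP as deviation) | 20/26 = 76.9% | 33/55 | 0.321 / 0.132 = 2.43 | 0.015 |
| LOCF as lice free (mITT) | 23/29 = 79.3% | 36/58 | 0.345 / 0.127 = 2.71 | 0.007 |

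The PP row assumes no other PP exclusions. All lice-free counts are at least 10, so the small-count alternative in 10.1 does not apply.

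**4. Same case near the design effect.** With 25 other spray successes the rates are 25/29 = 86.2%, 25/26 = 96.2% and 28/29 = 96.6%. All give p of about 0.001 or less.

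**5. Opposite direction.** Spray is 25/29, and four of the 16 control failures use another product. As failures: 13/29, difference 41 points, p = 0.0009. Carried forward: 17/29 = 58.6%, difference 28 points, p = 0.019. Dropped: 13/25 = 52.0%, difference 34 points, p = 0.006. The estimate moves by 7 to 14 points and significance is kept.

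**6. Is the early reading a fair stand-in?** After a single application the pilot was 88% lice free on the day of treatment and 12% at Day 14. A subject discontinued before Day 7 has likewise had one application. Carrying Day 2 forward therefore assumes a persistence that the sponsor's own data contradict.

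**The case against.** The strongest reply is that 10.2 already covers most of these subjects. Lice free at Day 2, live lice on Day 5 and then another product is a worsening followed by alternate therapy, hence a failure in both populations. If live lice were present at the last visit, LOCF itself gives a failure, and so does item 5 of 5.5.1. This stands. The gap is confined to subjects last seen lice free whose relapse is not recorded, or whose use is not judged to have been required.

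A reader might infer that these subjects can also fall out of mITT, by joining item 7 of 5.5.1 to the untimed eligibility condition. The documents do not support that well. Eligibility is verified at Day 0 (7.3.1, 16.1), the mITT definition lists it before randomization and treatment, and 10.2 expressly keeps early discontinuers in mITT. Read without limit, the synopsis exclusion on treatment after diagnosis would cover the study products themselves. What remains is a missing time point, which one sentence can supply.

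A reader might likewise infer that a scalp reaction after dosing removes a subject from mITT. That criterion is worded for presentation at the site, and later reactions fall under the adverse event items.

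It is also fair to say that counting any product use as failure makes the Day 14 endpoint a composite. A subject who is lice free on examination could be scored as a failure.

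**Conclusion.** The point holds in a limited form. Section 10.2 gives no explicit rule for prohibited-product use, and its two-condition failure trigger combined with LOCF can credit a self-treated subject with success in mITT. PP gives two answers for the same subject. The ambiguity lies among the sentences of 10.2; 5.5.1 only triggers the discontinuation, so this is not a contradiction between separate sections.

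The size is 3.4 points per affected subject in an arm of 29. In the assumed case of three spray subjects, the rule alone takes p from 0.063 to 0.007. That rests on assumed counts and on all three being last seen lice free. A reader might infer that a real difference would be hidden. The control-arm example does not show that, since significance survives (p = 0.019 or 0.006), and at the full design effect the conclusion is unchanged. The rule matters when the true effect is smaller than planned, and it affects the estimate in any case.

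**What to change.** Amend 10.2, as an analysis definition only, leaving clinical management untouched:

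1. Any use of a non-study lice product between first application and the Day 14 examination counts as not lice free at Day 14, in both arms and in both mITT and PP, whether or not worsening was recorded. Report LOCF or observed status as a sensitivity analysis.
2. mITT eligibility is judged only on facts existing before first application.

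A cross-reference from 5.5.1 items 4 and 7 to this rule would help.

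The cost is a few sentences. Medication use is already asked about at every visit (7.1, 7.4), so no new data are needed, and the sample size stays at 58. The downside is that a few subjects who are lice free on examination would count as failures, slightly lowering an arm's rate; the sensitivity analysis shows by how much.

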5.5.2 Handling of Subject Withdrawals or termination

The Sponsor reserves the right to discontinue the trial prior to inclusion of the intended number of subjects. After such a decision, the Investigator must contact all participating subjects within a time period specified by the Sponsor to inform them of the decision to discontinue the trial.

5.6 Premature suspension or Termination of Study

The following criteria may result in either temporary suspension or early termination of the study:

- New information regarding the safety or efficacy of the investigational product that indicates a change in the known risk/benefit profile for the compound, such that the risk/benefit is no longer acceptable for subjects participating in the study.
- Significant violation of GCP that compromises the ability to achieve the primary study objectives or compromises subject safety.

The Sponsor reserves the right to discontinue the trial for other valid administrative reasons.

Criteria for Premature Termination or Suspension of Investigational Sites:

- A study site may be terminated prematurely or suspended if the site (including the Investigator) is found to be in significant violation of GCP, protocol, contractual agreement.

Procedures for Premature Termination or Suspension of the Study or Investigational Site(s):

- In the event that the Sponsor elects to terminate or suspend the study or the participation of an investigational site, a study-specific procedure for early termination or suspension will be provided by the Sponsor; the procedure will be followed by applicable investigational site during the course of termination or study suspension.
- Appropriate therapy and follow-up should be ensured for any study subject by the sponsor.
- Ensure where required by applicable regulatory requirements that the regulatory authority is properly informed.
- If the sponsor terminates the study or the subject withdraws, the end of treatment visit and/or discontinuation Visit should be conducted.

6. Study product

6.1 Study product and control description

6.1.1 Acquisition

The drug depot will receive study products and perform IP accountability and monitoring, including assurance of adequate contents and quantities, based upon the IP packing list. For acquisition of study products at the clinical site, study products will be shipped to clinical site through the designated drug depot. The drug depot will provide initial study products for study initiation and resupply thereafter, as needed

6.1.2 Formulation, appearance, packaging and labeling

Document Attached: Alliance Pharma - Vamousse Spray 'n' Go 4oz Label

The test product is Vamousse Spray 'n' Go manufactured by Alliance Pharmaceuticals Ltd., supplied in 4 oz. tubes.

Study product Spray:

Active ingredient: Natrum Muriaticum 2X (HPUS)

Inactive ingredients: Benzyl Alcohol, Geraniol, Glycerin, Isopropyl Alcohol, Linalool, Potassium Cocoate, Water.

The control product is Nix Creme Rinse Lice Treatment manufactured by Prestige Consumer Healthcare Inc., supplied in 2 oz. bottles.

Control product Shampoo:

Active ingredient: Permethrin 1% shampoo

Inactive ingredients: balsam canada, cetyl alcohol, citric acid, FD&C yellow no. 6, fragrance, hydrolyzed animal protein, hydroxyethylcellulose, polyoxyethylene 10 cetyl ether, propylene glycol, stearalkonium chloride, water, isopropyl alcohol 5.6 g (20%), methylparaben 56 mg (0.2%), and propylparaben 22 mg (0.08%).

6.1.3 Product Storage and Stability

Store at room temperature 20°C to 25°C (68°F to 77°F; excursions permitted to 15° to 30°C (59°F to 86°F. Do not freeze. All study drug supplies will be kept in a secure cabinet or room with controlled access. Only the designated study personnel will have access to study drug supplies.

The Investigator will maintain temperature monitoring of the study products with daily temperature readings. All temperature excursions must be reported to the Sponsor using the Temperature Excursion Form. If the study drug was exposed to the temperature excursion outside the range 15-30°C, or within this range, but for the period greater than 24 hours, the study drug must be quarantined until the Medical Monitor / Sponsor's approval on future use. Please refer to the Pharmacy Manual for additional detail on the Temperature Excursions and temperature monitoring during the shipment and storage at the site pharmacy.

6.1.4 Preparation

Shake the bottle to ensure the product is fully mixed. Neither Vamousse Spray 'n' Go nor the Nix requires no additional preparation prior to use.

6.1.5 Dosing and administration

Lice and nit removal is not performed prior to nor during dosing and administration. For the study drug (Vamousse Spray 'n' Go), separate hair into 3-4 sections with clips. Part hair in 1-inch sections, spray treatment to completely saturate each section. Work through hair with a comb to ensure full coverage down to the scalp. Pay special attention to the nape of the neck and behind ears. Thoroughly saturate all hair and scalp. To be effective, all lice and nits must come in contact with the product. Allow hair to dry naturally. Leave treatment in for a minimum of 8 hours. Avoid contact with eyes. Do not swallow. Thoroughly wash hands after applying study product. Vamousse Spray 'n' Go should be used in the context of an overall lice management program:

- Wash (in hot water) or dry-clean all recently worn clothing, hats, used bedding and towels.
- Wash (in hot water) personal care items such as combs, brushes and hair clips.

For the control drug (Nix Creme Rinse Lice Treatment), first shampoo the hair and scalp using regular shampoo. Then thoroughly rinse and towel dry the hair and scalp, and allow hair to air dry for a few minutes. Shaking the permethrin lotion well before applying, proceed to thoroughly wet the hair and scalp with the permethrin lotion, being sure also to cover the areas behind the ears and on the back of the neck. After allowing the lotion to remain in place for 10 minutes, rinse the hair and scalp thoroughly and dry with a clean towel.

6.1.6 Route of Administration

Vamousse Spray 'n' Go, is for topical use only. It is not for oral, ophthalmic, or intravaginal use.

6.1.7 Duration of therapy

The study is comprised of three phases: Screening, Treatment (3) Follow-Ups. The duration of this study is 14 days (+/- 3). The Screening and Treatment Phase (baseline) will be Day 0 (visit 1). Screening and treatment will occur on the same day.

6.1.8 Tracking of at home compliance

Subject Home Instructions will be distributed and accounted for. Subjects will fill out their Subject Home Instructions noting the following:

- Time and date of removal (washing off the study drug in 8 hours, followed by thorough combing)
- Confirmation that subject disinfected personal items; worn clothing, hats, used bedding and towels
- Confirmation Wash (in hot water) or dry-clean all recently worn clothing, hats, used bedding, towels including combs, brushes and hair clips.

Subjects will return their Subject Home Instructions to the clinical site for compliance review at Follow-up Day 2, Day 7, and Day 14. The Investigator will verify that the subject complied with disinfection regimen. Both the subject and the study staff will sign off on completed Subject Household Instructions. If the subject has missed the disinfection notation, this is considered a protocol deviation and must be reported.

